11.2.11 Proportion of patients with multiorgan failure at 1 month

The proportion of patients with multiorgan failure will be defined as the number of patients with multiorgan failure during their hospitalization measured at 1 month over the number of evaluable patients.

11.2.12 Time to improvement in NEWS2 score ≤ 2

Determine the time to improvement in NEWS score will be defined as time from start of treatment until NEWS score ≤ 2 and maintained for at least 24hrs. The NEWS 2 score is calculated based respiratory rate, oxygen saturation, systolic blood pressure, pulse rate, level of consciousness/confusion and temperature.

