5.1 Inclusion Criteria

- Male or female adult ≥ 18 years of age at time of enrollment.
- Confirmed diagnosis of SARS-CoV-2 infection ≤ 14 days prior to registration.

- Inpatient hospitalization (or documentation of a plan to admit to the hospital if the patient is in the emergency department)
- Evidence of pneumonia by chest radiographs, chest CT **OR** chest auscultation (rales, crackles).
- Severe respiratory disease (oxygen saturation $\leq 93\%$ on room air or requires $\geq 2\text{L}$ oxygen by NC in order to maintain $\text{SaO}_2 \geq 93\%$) **OR** critical respiratory disease (requiring non-rebreather, non-mechanical/mechanical ventilation, high-flow nasal cannula, ICU admission).
- Patients can continue their anti-cancer therapy at the discretion of the treating physician.
- *Adequate laboratory tests including:*
 - ANC $>500 \text{ cells/mm}^3$
 - Platelet count $>20,000 \text{ cells/mm}^3$
 - Serum total bilirubin $<1.5 \times \text{ULN}$
 - ALT $<5 \times \text{ULN}$
 - AST $<5 \times \text{ULN}$
- *Age and Reproductive Status*
 - a) Males and females, aged at least 18 years old
 - b) Women of childbearing potential (WOCBP) must have a negative serum or urine pregnancy test (minimum sensitivity 25 IU/L or equivalent units of human chorionic gonadotropin) within 24 hours prior to the start of study treatment.
 - c) Women must not be breastfeeding.
 - d) WOCBP must agree to follow instructions for method(s) of contraception for the duration of study treatment plus for a total of 155 days post treatment completion. Local laws and regulations may require use of alternative and/or additional contraception methods.
 - e) WOCBP who are continuously not heterosexually active are also exempt from contraceptive requirements, but should still undergo pregnancy testing as described in this section.
 - f) Males who are sexually active with WOCBP must agree to follow instructions for method(s) of contraception during study treatment with BMS-986253 for a total of 215 days post-treatment completion.
 - g) Azoospermic males are exempt from contraceptive requirements. WOCBP who are continuously not heterosexually active are also exempt from contraceptive requirements, and still must undergo pregnancy testing as described in this section.
- Willingness to provide written informed consent and HIPAA authorization for the release of personal health information, and the ability to comply with the study requirements

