10. STUDY CALENDAR

Every effort should be made to keep visits, tests, and procedures on schedule. Acceptable deviations are listed below.

	Screening Evaluation ^a	During Hospitalization (daily unless indicated)	Day 29 and Follow-up (after discharge) ^f
Informed consent	X		
Medical history (including baseline ECOG)	X		X
Review of medications	X	X	X
Physical assessment ^k	X	X	
Vital signs (including SpO ₂ /FIO ₂ if on supplemental oxygen)	X	(3 times per day) ⁱ	
Height and weight	X		
Laboratory studies ^b	X	X	
Inflammatory markers ^j	X	Every 2 days	
NLR and absolute lymphocyte count	X	X	
Serum ^c	X	Every 7 days (+/- 2 days) ^c	
NEWS2 score ^d	X	X	
7-point ordinal scale ^l	X	X	
Chest imaging (optional) ^e	X	Every 7 days (+/- 2 days) ^e	
BMS-986253 dose		Every 2 weeks for 1-3 doses ^g	
Toxicity assessment		X	X ^h

a: The screening (pre-treatment) evaluation should be conducted within 1 day prior to dose of BMS-986253. If screening done on same day as treatment then treatment day 1 assessments do not need to be repeat (screening assessments will suffice)
b: Laboratories should include hemoglobin, hematocrit, white blood cell count with differential (including absolute eosinophil count), platelets, sodium, potassium, chloride, bicarbonate, urea nitrogen, creatinine, glucose, calcium, albumin, total protein, bilirubin, alanine aminotransferase (ALT), aspartate aminotransferase (AST), alkaline phosphatase. Prothrombin time (PT/INR), activated partial thromboplastin time (APTT) will be drawn at baseline and then as clinically indicated.
c: Serum samples should be collected for cytokine and PK analysis at screening, day 8, 15, 22, 29, and EOT if possible (not required). Should be collected prior to the treatment dose of day 15 and 29. For patients ready for discharge prior to day 8, a serum sample should be collected, when feasible, prior to discharge.
d: NEWS2 score is calculated considering respiratory rate, oxygen saturation, systolic blood pressure, pulse rate, level of consciousness/confusion, temperature.
e: CT chest or CXR at baseline (within 2 days of enrollment) and after 7 days (+/- 2 days) if clinically indicated.
f: Can be done by phone: at day 29 (+/- 1 day) and every 1 month (+/- 1 week) (until 100 days following last dose of treatment), then every 3 months (+/- 1 month) from registration to up to 1 year follow up.

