- review of medication list daily
- review of toxicity/adverse events daily
- vital signs (pre- and post-infusion of BMS-986253) and three times per day including temperature, heart rate, blood pressure, respiratory rate, oxygen saturation and FIO₂ and SpO₂/FIO₂ if on supplementation oxygen.
- physical exam daily
- hematological laboratories (hemoglobin, hematocrit, white blood cell count with differential [including absolute eosinophil count], platelets) daily
- coagulation profile (INR, aPTT) as clinically indicated.
- serum chemistry profile (sodium, potassium, chloride, bicarbonate, urea, creatinine, glucose, calcium, albumin, total protein, bilirubin, ALT, AST, alkaline phosphatase) daily
- CRP, D-Dimer, LDH, sIL-6 level every other day
- Neutrophil-to-lymphocyte ratio (NLR), absolute lymphocyte count daily
- NEWS2 score daily
- 7-point ordinal score daily
- CT or CXR of the chest weekly (+/- 2 days) (optional)
- Sera for biomarker and PK analysis day 8, 15, 22, 29, and EOT (+/- 2 days). Where possible, the Day 15 and 29 PK samples should be collected just prior to dosing (optional). For patients ready for discharge prior to day 8, a serum sample should be collected, when feasible, prior to discharge.
- Patients randomized to anti-IL-8 therapy will receive BMS-986253 every 2 weeks (+/- 2 days) x 1-3 doses, with 2nd dose given if patient still hospitalized and then 3rd dose optional if patient still hospitalized with severe COVID-19. Patients randomized to control will receive standard of care.

10.3 Follow-Up After Discharge:

Following completion of therapy, patient will have follow up by phone every 30 days for the first 100 days following the last dose of therapy. Patients will then have follow up by phone every 90 days (+/- 30 days) for up to 1 year. In addition, patients will be assessed 28 days (+/- 2 days) following start of treatment whether they are discharged or in the hospital. These assessments will include:

- review of medication list
- review of toxicity/adverse events (for up to 100 days following last dose of treatment)
- Evaluation of Katz basic ADLs and Lawton IADLs (Appendix C and D)

- assessment for survival

Patients withdrawing from the study early because of adverse events should be followed until the adverse event has either resolved or stabilized. Reasons for premature withdrawal should be determined and documented.

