11.2 Secondary Endpoints

11.2.1 *Time to death*

The time to death will be defined as the time from onset from symptoms until death from any cause. Patients who are alive or lost to follow-up at the cut-off date will be censored from this analysis.

11.2.2 *Mortality at 1 month*

1-month mortality is defined as the percentage of patients who have died 1 month from the time of start of treatment.

11.2.3 *Time to intubation*

The time to intubation will be defined as the time from symptom onset until time of intubation. Any patients already intubated at enrollment will be censored from this analysis.

11.2.4 *Time to improvement in oxygenation*

The time to improvement in gas exchange will be defined as the time from time of start of treatment until a $\geq 30\%$ decrease in oxygen requirement compared to

baseline [or elimination of oxygen requirement] without a decrease in SpO2 sustained for at least 48hrs or until discharge.

11.2.4 *Proportion of patients requiring ICU admission at 1 month.*

The proportion of patients requiring ICU admission will be calculated as the number of patients requiring ICU admission over the course of their hospitalization over the number of evaluable patients.

11.2.5 *Safety and Toxicity*

All subjects receiving at least one dose of the study drug will be evaluated for safety by monitoring symptoms, physical examinations, and laboratory tests. Adverse events will be classified and graded according to the NCI Common Toxicity Criteria version 5.0 (see Appendix A). The absolute number and frequency of each adverse event will be reported, and subdivided according to toxicity grade. A description of adverse events by treatment arm will also be reported. A particular adverse event occurring more than once in the same subject will be counted only once and at its worse grade.

11.2.6 *Duration of Hospitalization*

Duration of hospital admission will be measured from the time of admission until the time of discharge.

11.2.7 *7-point Ordinal Scale Score*

The mean/medians of the 7-point ordinal raw scores at day 14 from the start of treatment will be computed and compared between the treatment and control groups.

Exploratory Endpoints.

11.2.8 *Change in inflammatory markers from baseline*

Changes in LDH, D-Dimer, CRP, ESR, NLR and absolute lymphocytes before and after treatment and over time will be measured every other day during hospitalization.

11.2.9 *Change in circulating sIL-6 levels from baseline*

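### Exploratory time to NEWS2 ≤ 2: the listed items conflict with Appendix B on oxygen, some eligible patients may already be at the threshold, and the 24-hour hold cannot be confirmed after discharge

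*Combined protocol and SAP*

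**What the plan says.** Time to NEWS2 of 2 or less is one of the exploratory objectives in Section 2.1. Section 11.2.12 (the first of two sections with that number) defines it as "time from start of treatment until NEWS score ≤ 2 and maintained for at least 24hrs". It sets no condition on the baseline score and does not mention discharge.

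The same section says how the score is built: "The NEWS 2 score is calculated based respiratory rate, oxygen saturation, systolic blood pressure, pulse rate, level of consciousness/confusion and temperature". Footnote d of the Study Calendar in Section 10 gives the same six items: "NEWS2 score is calculated considering respiratory rate, oxygen saturation, systolic blood pressure, pulse rate, level of consciousness/confusion, temperature". The scoring chart in Appendix B has a seventh row, for air or oxygen, which gives 2 points on oxygen and 0 on air.

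Section 5.1 admits patients by several routes. Two of them are set by saturation: "Severe respiratory disease (oxygen saturation $\leq 93\%$ on room air", or at least 2 L of "oxygen by NC in order to maintain" a saturation of at least 93%. No entry criterion sets a minimum NEWS2.

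In hospital, Section 10.2 schedules "NEWS2 score daily". After discharge, Section 10.3 says: "Following completion of therapy, patient will have follow up by phone every 30 days for the first 100 days". The assessments listed there are medications, toxicity, activities of daily living and survival. The Study Calendar also leaves the NEWS2 row blank in the follow-up column.

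The oxygenation endpoint in Section 11.2.4 handles discharge explicitly: "without a decrease in SpO2 sustained for at least 48hrs or until discharge".

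**The concern.** An endpoint of time to recovery should start with everyone short of the target, use one scoring rule, and be observable in patients who do well. This definition leaves a gap on each count.

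- **Scoring rule.** The item list and the chart differ by 2 points for anyone on oxygen, and 2 points is the whole threshold.
- **Starting point.** The heading speaks of improvement, but the definition asks only for a level. A patient at that level on entry needs no improvement to become an event.
- **Observability.** The 24-hour hold needs a later score, and none is scheduled once the patient has left hospital.

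What is at stake is how this one exploratory comparison is read. There is also a choice between two scoring rules that would otherwise be made after the data are in.

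**Working it through.** The plan states no figure on this point, so there is none to reproduce. The check scores the two saturation-based entry routes on the Appendix B chart and then compares the 24-hour rule with the visit schedule.

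**Inputs from Appendix B.** SpO2 Scale 1: 91% or less = 3, 92–93% = 2, 94–95% = 1, 96% or more = 0. Oxygen = 2, air = 0. All other items are set to 0: respiratory rate 12–20, pulse 51–90, systolic pressure 111–219, alert, temperature 36.1–38.0 °C.

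**Step 1: score at entry, Scale 1.** Seven-item score = SpO2 points + oxygen points. Six-item score = SpO2 points only.

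| Entry state | Seven items (Appendix B) | Six listed items |
|---|---|---|
| Air, SpO2 ≤ 91% | 3 + 0 = 3, not met | 3, not met |
| Air, 92–93% | 2 + 0 = 2, met | 2, met |
| Cannula, 93% | 2 + 2 = 4, not met | 2, met |
| Cannula, 94–95% | 1 + 2 = 3, not met | 1, met |
| Cannula, ≥ 96% | 0 + 2 = 2, met | 0, met |

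Under Appendix B, two eligible groups sit at the threshold on entry. Under the six-item list, every qualifying cannula saturation does. A score at the threshold becomes an event only if it then holds for 24 hours.

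**Step 2: what the missing row changes.** Dropping it subtracts 2 from every on-oxygen score. Classification therefore changes for patients on oxygen whose seven-item score is 3 or 4 (3 − 2 = 1 and 4 − 2 = 2). Take a stable patient on high-flow oxygen at 94% with all else normal. The chart gives 1 + 2 = 3, not met; the list gives 1, met. The primary ordinal scale in Section 11.1.1 puts this patient in category 3. At 96% or more on high flow, both rules meet the threshold (0 + 2 = 2 and 0), so restoring the row narrows this overlap but does not remove it.

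**Step 3: the other saturation scale.** Appendix B also prints Scale 2, and the plan does not say which scale applies. On Scale 2, air at 88–93% scores 0 and air at 86–87% scores 1, so the threshold is met. Cannula at 93–94% scores 1 + 2 = 3, at 95–96% 2 + 2 = 4, and at 97% or more 3 + 2 = 5, none met. With six items those cannula scores are 1, 2 and 3, so the threshold is met up to 96%. The overlap at entry is present on either scale, but in different patients.

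**Step 4: the 24-hour hold against the schedule.** Scores are daily and in hospital only. A patient who first scores 2 or less and is discharged less than 24 hours later has no further scheduled score, so the hold cannot be shown. Section 13.2 applies Kaplan-Meier, log-rank and Cox methods to all time-to-event endpoints but gives no rule for this case. The patient could be kept as a non-event or censored at discharge. Censoring at discharge would be informative, because discharge is related to recovery.

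**The case against.** The strongest reply is that little hangs on this. The endpoint is one of ten exploratory objectives and carries no alpha, power or stopping rule. That stands, and it sets the weight of the point.

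It can also be said that the six-item text does not define the score. It assigns no points, and Appendix B is the only scoring chart in the document, so a scorer must use it and would meet the oxygen row there. This stands in part. A reader might infer that the plan deliberately scores NEWS2 without oxygen; the documents do not support that. They contain a list and a chart that disagree. The chart cannot simply be presumed to govern, however: neither Section 11.2.12 nor footnote d cites Appendix B, and Section 13.6 cites it for the toxicity criteria.

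On the overlap at entry, the group is narrow. It needs particular saturations with every other item at zero, the score must then hold for 24 hours, and the air case applies only to patients still on air when baseline is scored. Eligibility also covers non-rebreather, high-flow, ventilated and ICU patients. A reader might want to put a count on events at time zero, but the plan gives no baseline NEWS2 distribution, so no count can be supported. Randomization also means such patients are expected in both arms in proportion, so the expected result is dilution and not a tilt toward one arm.

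On discharge, a reader might infer that the fastest recoveries are lost and the endpoint is biased against the drug. That goes too far. What matters is the interval from first reaching 2 or less to discharge. A patient who reaches it on day 1, holds it and leaves on day 3 is counted. No frequency is given for early departures, and the text does not say whether they are censored or kept as non-events.

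**Conclusion.** The concern holds as a minor one, in three parts.

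1. The item lists in Section 11.2.12 and footnote d conflict with Appendix B. Following the lists lowers every on-oxygen score by 2, enough for a stable patient on high-flow oxygen to meet the threshold when the chart would say otherwise.
2. Some eligible patients can score exactly 2 at entry under Appendix B (Scale 1, other items normal: 92–93% on air, or at least 96% on cannula). If stable for 24 hours they are events at or near time zero and carry little or no treatment information. Their number is unknown; the expected effect is dilution.
3. A patient discharged within 24 hours of first reaching 2 or less cannot be confirmed as an event. If discharge is earlier in one arm, this could bias against that arm, by an amount the documents do not allow one to estimate.

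The scores follow from the Appendix B chart. The third part rests on no NEWS2 being scheduled after discharge. The primary analysis, the sample size and the interim boundaries do not use this endpoint and are unaffected.

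**What to change.** - In Section 11.2.12 and Study Calendar footnote d, list all seven Appendix B items, including air or oxygen, and cite Appendix B. State which SpO2 scale applies.
- Analyse this endpoint in patients whose baseline seven-item NEWS2 is above 2. Because the restriction uses a baseline value, it keeps the randomized comparison within that group.
- Define the event as NEWS2 of 2 or less maintained for 24 hours or until discharge alive, in parallel with the oxygenation endpoint in Section 11.2.4.

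The cost is wording and programming. Oxygen saturation, and FIO2 when on supplemental oxygen, are already recorded with vital signs three times a day, so the oxygen row can be scored without new data collection. The downside is that patients with a baseline score of 2 or less drop out of this one exploratory analysis. The changes should be made before the data are analysed, so that the choice between scores 2 points apart is not made afterwards.

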11.2.13 To measure time on ventilation

Measured from time of intubation to time of definitive extubation. Will censor for patients not requiring intubation.

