Exploratory:	
• To assess the change in LDH, D-Dimer, CRP, ESR, NLR and absolute lymphocytes before and after treatment and over time (every 2 days for duration of hospitalization).• To assess the change in sIL-6 before and after treatment and over time.• To evaluate radiological response by comparing % of lung fields with infiltrates on chest imaging (CXR and CT) through independent radiology review.• To measure time on ventilation measured from time of intubation to time of definitive extubation• To measure time to improvement in NEWS2 score to ≤ 2• To evaluate the change in NEWS2 from baseline.• To measure proportion of patients with multi-organ failure at 1 month.• To assess whether IL-8 and other key cytokines (TNF, IL-1b, IL-6) at baseline and during treatment are predictive of treatment efficacy by quantification of circulating IL-1b, IL8, TNFalpha and IL-6 levels over time.• To quantify changes in humoral immune responses by antibody profiling at baseline and following treatment.• To characterize PK of BMS-986253 in cancer patients with severe COVID-19.

Diagnosis and Main Inclusion Criteria	Main Inclusion Criteria 
Confirmed diagnosis of SARS-CoV-2 infectionInpatient hospitalization due to SARS-CoV-2 infectionSevere (oxygen saturation $\leq 93\%$ on room air or requires $\geq 2\text{L}$ oxygen by NC in order to maintain $\text{SaO}_2 \geq 93\%$) OR critical respiratory disease (ICU, ventilatory support, HFNC)Non-COVID-related life expectancy > 2 monthsWillingness to provide informed consent
Study Product, Dose, Route, Regimen	BMS-986253 2400mg IV at 0 and 2 weeks (if patient is still hospitalized) and then 4 weeks (only if continued severe respiratory disease).
Duration of administration	Every 2 weeks x 1-3 doses.
Reference therapy	Standard of care management

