13.2 Study Endpoints and Analysis Plan

All subjects who receive at least one dose of study drug will be considered evaluable and included in the efficacy and safety analysis.

Analytic plan for primary objective:

The primary efficacy null hypothesis of the equality of time to improvement (2 points) in clinical status curves will be tested with the log-rank test. The overall type I error for the primary analysis will be considered one-sided alpha of 0.025. Kaplan-Meier estimates will be reported for each of the two arms with median time to improvement and 95% confidence intervals (CI). Cox regression will be employed to estimate the treatment effect (HR) and 95% CI.

Analytic plan for secondary and exploratory objective:

We will estimate the distributions of all time-to-event endpoints using the Kaplan-Meier method and if possible, provide medians (95% CI). Comparisons between survival curves will be assessed using log-rank tests and Cox regression models.

For each arm, we will estimate the 1-month mortality rate and incidence of adverse events graded by CTCAE v5.0 using the exact 95% confidence intervals. Comparisons between the two arms will be assessed using chi-squared or Fisher's exact tests. The mean/medians of the 7-point ordinal scores at day 14 after the start of treatment will be computed and compared between the two groups using two-sample t-test or the equivalent non-parametric Wilcoxon Rank-Sum test if normality is not satisfied.

Changes in exploratory endpoints (before and after treatment) will be quantified using means (95% CI) and/or medians (inter-quartile ranges) for non-normal data. Comparisons between the two arms will be made using two-sample independent t-tests or the non-parametric equivalent, Wilcoxon Rank-Sum test. The associations between baseline levels and/or changes over time of IL-8 and other key cytokines (TNF, IL-1b, IL-6) with outcomes will be assessed using regression models.

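### Exploratory time on ventilation is compared only among intubated patients, a group the drug may partly shape, and death on the ventilator has no rule

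*Combined protocol and SAP*

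**What the plan says.** Time on ventilation is listed among the exploratory objectives (synopsis and Section 2.1). Section 11.2.13 sets the clock: "Measured from time of intubation to time of definitive extubation". It then handles the remaining patients in one sentence: "Will censor for patients not requiring intubation". No censoring time is given, and death before extubation is not mentioned.

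The analysis comes from the paragraph of Section 13.2 that covers secondary and exploratory objectives together: "We will estimate the distributions of all time-to-event endpoints using the Kaplan-Meier method", followed by "Comparisons between survival curves will be assessed using log-rank tests and Cox regression models".

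Two other places matter. Section 5.1 admits patients with "critical respiratory disease (requiring non-rebreather, non-mechanical/mechanical ventilation, high-flow nasal cannula, ICU admission", so some patients can be on a ventilator at entry. Section 11.2.3 makes time to intubation a secondary endpoint, so the plan itself treats intubation as something the drug might alter. For that endpoint it says: "Any patients already intubated at enrollment will be censored from this analysis". Section 11.2.13 makes no such distinction by status at entry.

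**The concern.** A patient who is never intubated cannot be at risk of extubation. Censored at time zero, that patient drops out of every risk set. Censored at any later time, the patient is counted as ventilated and not yet extubated, which is a different error and would make the arm with fewer intubations look slower to extubate. Under the workable reading, the comparison is between the intubated patients of each arm.

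Membership of that group is fixed at entry for some patients and decided after randomization for the others. Randomization does not balance the second part if the drug changes who is intubated. Avoiding intubation, the best result for a patient, removes that patient from the comparison. If the patients spared are those who would have had short ventilation, the treated arm keeps the longer cases, and the result can point to harm where there is benefit.

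Two gaps add to this. For patients ventilated at entry, the measured time includes days before randomization. For patients who die on the ventilator, censoring treats them as still able to be extubated, while ending the clock at death makes early death look like short ventilation. Section 3.1 cites mortality of roughly 20 to 25% in severe disease, so this will arise.

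**Working it through.** The documents give no intubation rate, ventilation time or target effect for this endpoint, so there is no planned figure to reproduce. The check asks what the stated rule returns when the drug changes who is intubated but no one's duration.

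**From the documents:** 2:1 allocation, 92 and 46 patients (Section 13.1); start and stop of the clock (11.2.13); Cox comparison (13.2); ventilated patients eligible (5.1).

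**Assumed:** 20 to 30% of control patients not ventilated at entry are later intubated. The drug prevents 25 to 50% of these, all of the shorter kind. Durations are exponential with mean 14 days for the longer kind and 5 to 7 days for the shorter. Patients ventilated at entry have mean 14 days. Follow-up stops at 28 days. There are no deaths.

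**Central case by hand** (30% intubated, half of them short at 7 days, none ventilated at entry):

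- Mean duration per intubated patient: control 0.5 × 14 + 0.5 × 7 = 10.5 days; drug 14 days.
- Mean within 28 days: longer kind 14 × (1 − e^−2) = 12.1 days; shorter kind 7 × (1 − e^−4) = 6.87 days.
- Ventilator days per randomized patient: control 0.15 × 12.1 + 0.15 × 6.87 = 2.85; drug 0.15 × 12.1 = 1.82.

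Per intubated patient the drug looks worse; per randomized patient it is better.

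**Simulation** (920,000 drug and 460,000 control patients, Cox model among the intubated only, none ventilated at entry). A hazard ratio below 1 means slower extubation on drug.

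| Control intubated | Share prevented | Mean days, longer / shorter kind | Extubation HR | Median days, drug vs control | Ventilator days per randomized patient, drug vs control |
|---|---|---|---|---|---|
| 20% | 25% | 14 / 7 | 0.86 | 9.7 vs 8.0 | 1.81 vs 2.15 |
| 30% | 33% | 14 / 7 | 0.82 | 9.7 vs 7.5 | 2.41 vs 3.09 |
| 30% | 50% | 14 / 7 | 0.74 | 9.8 vs 6.8 | 1.82 vs 2.85 |
| 30% | 50% | 14 / 5 | 0.67 | 9.6 vs 5.6 | 1.81 vs 2.55 |
| 30% | 50% | 14 / 14 | 1.00 | 9.7 vs 9.7 | 1.82 vs 3.63 |

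**Patients ventilated at entry dilute the effect.** Over the first four rows the hazard ratio is 0.75 to 0.91 with 10% ventilated at entry and 0.81 to 0.94 with 20%. The last row stays at 1.00. Ventilator days per randomized patient are lower on drug in every scenario.

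**Precision at the trial's size.** In the central case about 92 × 0.15 = 14 drug and 46 × 0.30 = 14 control patients are intubated. With at most 14 extubations per arm, the standard error of the log hazard ratio is at least √(1/14 + 1/14) = 0.378. A 95% interval around 0.74 is then about 0.74 × exp(±1.96 × 0.378) = 0.35 to 1.55, or wider.

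The simulation quantifies neither the days before randomization nor the deaths.

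**The case against.** The best defence is that little depends on this endpoint. It is exploratory and carries no alpha, power or stopping rule. Its objective is to measure time on ventilation, without the comparison with controls that the secondary objectives state, and the log-rank and Cox sentence is generic. Time to intubation, time to death, one-month mortality, ICU admission and the day-14 ordinal score would show a reader that intubations had fallen. With about 14 intubated patients per arm, a misleading hazard ratio would be too imprecise to persuade anyone of harm.

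Most of this stands and limits the weight of the point. It does not remove it. The generic sentence sits in a paragraph that names exploratory objectives, so the between-arm test is planned as written. Imprecision does not correct a comparison that is not randomized. The rule for deaths is still missing.

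Stronger readings go too far. A reader might infer that the intubated group is formed wholly after randomization; the eligibility of ventilated patients contradicts that. A reader might build an extreme case: 30% of controls intubated, half for 7 days and half for 21, with the drug preventing every 7-day case. That gives 21 versus 14 days per intubated patient (7 days worse) against 3.15 versus 4.2 per randomized patient (25% better). The arithmetic is right, but nothing in the documents makes this the expected size. A reader might also extend the point to time to intubation and ask for intubation or death instead. Section 11.2.3 is silent on death before intubation, but mortality is analysed separately, and that composite is a different and debatable choice.

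**Conclusion.** The concern holds for the between-arm comparison of time on ventilation. As written, it conditions on a status the drug may change, mixes in time before randomization for patients ventilated at entry, and leaves death on the ventilator undefined.

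The direction of the error is possible, not certain. Apparent prolongation requires that the prevented intubations would have been shorter than the others; if they would have lasted as long, this bias is nil. All the sizes shown rest on intubation rates and durations that the documents do not give. A reader might infer that the trial's main conclusion is at risk. It is not: the primary log-rank test, its alpha and the sample size do not use this endpoint. This is a modest correction that protects an exploratory result from being read as harm, or as reassurance, that it cannot show.

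**What to change.** For the between-arm comparison, replace 11.2.13 with ventilator-free days from randomization to day 28 in all randomized patients. Rank death by day 28 strictly below a survivor with 0 ventilator-free days; scoring both as 0 would tie them. Compare the arms with the Wilcoxon rank-sum test already named in Section 13.2.

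The data are largely planned. The ordinal scale is scored daily in hospital, and its level 2 marks invasive ventilation or ECMO (Sections 10 and 10.2). All patients have an assessment including survival 28 days (±2) after the start of treatment (Sections 7.7 and 10.3). The text should add a convention for days after discharge, including readmission, and for aligning that visit with 28 days from randomization.

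Keep time on ventilation among intubated patients as a description without a test, split by ventilation status at baseline, with deaths on the ventilator counted separately.

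The cost is protocol and SAP wording, with no new visits or patients. The drawback is that ventilator-free days combine mortality and ventilation, so report both components beside it.
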